# 6.5 Exploratory Analyses

Mechanistic models of how treatment-related improvements in psychological (coping, fear of movement, adherence) and physical factors (objectively measured physical activity, biomechanical changes and fitness) explain changes in disability and pain outcomes across the three groups will be examined on an **exploratory basis**. Multiple path mediation analyses. 1) Selected indirect pathways between psychological coping skills, decreased fear of activity, and improved biomechanics (predictors), physical activity engagement and physical fitness (mediators), and functional disability and pain intensity (outcomes) will be tested for statistical significance within each of the three (FIT, CBT & GAE) groups, and 2) The magnitudes of the indirect effects will be tested for statistically significant differences between the three treatment groups. The False Discovery Rate will be used to maintain the nominal Type-1 error rate for all indirect effect tests.

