1. PURPOSE OF STUDY

A. Primary Objectives

Aim 1a: To test whether the combined FIT Teens intervention is more effective in reducing functional disability (primary outcome) than CBT alone or GAE alone.

H1a. The FIT Teens group will show significantly greater reduction in functional disability at 3-month follow-up compared to CBT and GAE, respectively.

Aim 1b: To test whether disability levels in the FIT Teens group are maintained at lower levels than CBT alone or GAE alone over time.

H1b. Functional disability in the FIT Teens group will remain significantly lower than CBT and GAE at 6-, 9- and 12-month follow-up.

Aim 1c: To test whether more patients who receive FIT Teens achieve clinically meaningful improvement in functional disability compared to those who receive CBT and GAE.

H1c. A significantly greater proportion of the FIT Teens group will achieve clinically meaningful reduction in functional disability (defined as $a \ge 7.8$ point reduction in FDI score) at 3-month follow-up than CBT and GAE.

Aim 2: To test whether the combined FIT Teens intervention is more effective in reducing pain intensity (secondary outcome).

H2. We hypothesize that the FIT Teens group will show significantly greater reduction in pain intensity at 3-month follow-up compared to CBT and GAE and that pain intensity in the FIT Teens group will remain significantly lower than CBT and GAE over time (6-, 9- and 12-month follow-up).

B. Secondary Objectives

Exploratory Aim: To examine a mechanistic model of how treatment-related improvements in psychological (coping, fear of movement, adherence) and physical factors (objectively measured physical activity, biomechanical changes and fitness) explain changes in disability and pain outcomes.

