Tests of the mechanisms that influence functional disability and pain intensity outcomes will be conducted using a multiple path mediation analyses. 1) All possible indirect pathways between psychological mechanisms (coping skills, decreased fear of activity, adherence) and physical assessments (biomechanics, physical activity and physical fitness) with the outcomes of functional disability and pain intensity will be tested for statistical significance within each of the three (FIT, CBT & GAE) groups via bias-corrected bootstrap testing of all indirect pathways, and 2) The magnitudes of the indirect effects will be tested for statistically significant differences between the three treatment groups via a multiple-group analysis. The False Discovery Rate will be used to maintain the nominal Type-1 error rate for all indirect effect tests.

J. Sample size and rationale (Power calculation)

The primary outcome for this RCT is reduction in functional disability. As such, the power calculations provided below are for the ability to detect whether FIT Teens results in significantly greater reduction in disability for Aims 1a, 1b and 1c.

Aim 1a. Differences between groups at the 3-month primary endpoint.

Power was calculated via the external Monte Carlo simulation capabilities in Mplus in two steps. First, 5000 dataset replications of hypothetical FDI scores were generated in a multiple group SEM format assuming: 1.) standardization of FDI scores, 2.) no differences in the three groups at baseline due to randomization (d = 0), 3.) group differences in FDI scores at 3 months, consistent with effect sizes from prior studies as follows: GAE (d = 0.40), CBT (d = 0.52), & FIT (d = 0.90), and 4.) N = 420 minus 20% attrition makes N = 336 (n = 112 per group) available for analysis assuming proper missing data handling. Second, the 5000 Monte Carlo replications were then analyzed using a longitudinal SEM assuming linear trend (i.e., slope loadings coded 0, 2, & 3) with dummy-coded CBT & GAE groups (FIT = reference). Results showed power ≥ 0.80 if the standardized 'slope on group' coefficient for either CBT or GAE is $\beta > 0.12$ assuming proper handling of cluster by site nesting as described above. With a revised sample size of N=315 (n=105 per group), our recalculated power analysis estimates power of >.80 for the GAE arm (versus reference group) and .79 for the CBT arm.

Aim 1b. Maintenance of treatment gains over follow-up.

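### The exploratory mechanism analysis uses randomised arm only as a grouping variable, never as the exposure, so it does not test whether treatment-induced change explains the outcomes

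*SAP*

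**What the plan says.** Protocol 1.B sets the exploratory aim: "To examine a mechanistic model of how treatment-related improvements in psychological" and physical factors explain change in disability and pain. SAP 6.5 repeats it ("how treatment-related improvements in psychological (coping, fear of movement, adherence) and physical factors") and labels the work exploratory.

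SAP 6.5 then lists the variables: "Selected indirect pathways between psychological coping skills, decreased fear of activity, and improved biomechanics (predictors), physical activity engagement and physical fitness (mediators"), with functional disability and pain intensity as outcomes. Arm is not among the predictors. The analysis has two steps:

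- Step 1, running into step 2, in SAP 6.5: the paths "will be tested for statistical significance within each of the three (FIT, CBT & GAE) groups, and 2) The magnitudes of the indirect effects" are then compared between arms. Protocol 5.I adds the method for step 1: "groups via bias-corrected bootstrap testing of all indirect pathways".
- Step 2, in Protocol 5.I: "The magnitudes of the indirect effects will be tested for statistically significant differences between the three treatment groups via a multiple-group analysis".

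Both documents apply False Discovery Rate control to the indirect-effect tests. Neither says which visits supply the predictor, the mediator and the outcome. Random assignment does appear in a model in SAP 6.5.1, but that model is for imputation.

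**The concern.** An indirect effect of treatment has two parts: what treatment does to the mediator, and what the mediator does to the outcome. Inside one arm treatment is constant, so the first part cannot be estimated there. A within-arm path from coping through fitness to FDI says that patients whose coping improved also improved in fitness and FDI. A general good or bad spell that moves all three would give the same picture. There is no untreated arm, so only the randomised contrast can separate treatment-induced change from change that would have happened anyway.

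Step 2 brings the arms together but compares path strengths, which is moderation. If FIT works by raising coping further than CBT does, with the same benefit per unit of coping, the path strengths are equal and step 2 has nothing to find. The risk is that associations are reported as treatment mechanisms while a real mechanism behind a FIT advantage goes unseen.

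**Working it through.** The documents give no power, effect size or correlation for this aim, so there is no planned figure to reproduce. The structural point rests on the text alone. The calculations below show its size under stated assumptions.

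**Inputs from the documents.** 105 patients per arm (SAP 4.0, Aim 1a); 20% attrition, so 0.8 × 105 = 84 as a lower case; two-sided alpha 0.05 (SAP 6.0); biomechanics at four of seven sites (Protocol 4.A), so 4/7 × 105 = 60 if sites recruit equally.

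**Assumed, not in the documents.** Correlations and path values, as given below. Clustering, FDR control and the bootstrap were not simulated. An indirect effect counts as significant when each of its paths is.

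**A. No treatment effect, shared fluctuation only.** Let P (psychological change), M (fitness or activity change) and Y (FDI change) share one factor, with every pairwise correlation equal to r. Then the P-to-M path is r, the M-to-Y path given P is r/(1+r), and the apparent indirect effect is r²/(1+r):

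- r = 0.3: 0.09/1.3 = 0.069
- r = 0.4: 0.16/1.4 = 0.114
- r = 0.5: 0.25/1.5 = 0.167

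These are non-zero although treatment does nothing. A closed-form check at n = 105, r = 0.3:

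- first path: t = 0.3 × √103 / √(1 − 0.09) = 3.19, so power is Φ(3.19 − 1.96) = 0.89
- second path: 0.3/1.3 = 0.231, t = 0.231 × √102 / √(1 − 0.053) = 2.40, so power is Φ(0.44) = 0.67
- both: 0.89 × 0.67 ≈ 0.60

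Simulations agree. Ranges cover the three arms and separate runs; the last row also includes the closed form.

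| Patients per arm | r = 0.3 | r = 0.4 | r = 0.5 |
|---|---|---|---|
| 105 | 58–60% | 83–84% | 94–95% |
| 84 | 44–46% | 73–74% | 87–89% |
| 60 (biomechanics, assumed) | 27–29% | 51–56% | 73–76% |

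At r = 0.2 the rate is about 22% at n = 105 and 15% at n = 84. Across r from 0.2 to 0.5 the cross-arm test rejects in 1–5%, so it does not flag the artefact. FDR control would not remove it, because the within-arm associations are truly non-zero.

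**B. Real mediation with equal slopes.** FIT shifts the mean of P, and separately of M, by s SD. Both path slopes are 0.3 in every arm. The within-arm indirect effect is 0.3 × 0.3 = 0.09 in every arm whatever s is. The effect of arm on Y through M is (s + 0.3s) × 0.3 = 0.39s, which is 0.195 at s = 0.5. Only the second quantity responds to treatment. Results at n = 105:

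| Test | s = 0.3 | s = 0.5 | s = 0.8 |
|---|---|---|---|
| Within-arm path, FIT | 72% | 72% | 73% |
| Within-arm path, comparators | 72–73% | 73% | 72% |
| Cross-arm difference | 3% | 4% | 4% |
| Arm → M → Y, arm as exposure | 76% | 99% | 99% |
| Arm → P → M → Y | 57% | 93% | 98% |

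At n = 84 the last two rows are 65/96/98% and 46/85/93%. In setting A, both arm-as-exposure tests reject in about 2–6%.

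**The case against.** Several points on the other side stand, and they limit what may be concluded.

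- A reader might infer that treatment is absent from the model altogether. It is not: the multiple-group analysis uses arm to define the groups. What is missing is arm as the exposure.
- A reader might infer that the analysis is useless. Step 2 answers a legitimate but different question. The arms train different skills, so path strengths could differ; with path values of 0.5 in one arm and 0.2 in another, the cross-arm test rejected in 85% of simulated trials. The 3–5% depends on equal slopes.
- Enrolment requires high FDI and pain, so it is tempting to blame regression to the mean. Selection shifts the outcome mean, but that alone does not create a correlation within an arm. With stable traits, independent measurement error and selection on baseline FDI, a within-arm path was significant in 0.4% of 1,000 trials. The artefact needs fluctuation shared by mediator and outcome, which is plausible but assumed.
- Simulating a genuine predictor–mediator–outcome chain gives higher rates (74%, 96% and over 99% at paths of 0.3, 0.4 and 0.5). Those figures are power to find a real path and should not be quoted as an artefact rate.
- SAP Tables 3 and 4 report adjusted means by arm for fear of movement, coping, catastrophizing and depression, so a larger shift under FIT would be visible there. They do not cover fitness or biomechanics, and they do not link the shift to the outcome.
- The abstract mentions mechanisms as something also to be evaluated. The documents do not support reading them as a main product of the trial.

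**Conclusion.** The concern holds in a limited form. The stated aim concerns treatment-related improvement, and the two planned steps do not estimate it: one measures association within arms, the other differences in path strength. That conclusion follows from SAP 6.5 and Protocol 5.I without simulation.

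The percentages are illustrations. They depend on assumed correlations, independent patients, unadjusted tests and, in setting B, equal slopes and no mediator–outcome confounding. Paths using biomechanics or accelerometry will have fewer patients than the main cases assume; accelerometry was permanently dropped in October 2021.

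The stakes are modest because the aim is exploratory and no primary or secondary test depends on it. It is nevertheless worth correcting, since the needed visits are already scheduled.

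**What to change.** In SAP 6.5 and Protocol 5.I, add as the mechanism analysis the indirect effect of each randomised contrast (FIT vs CBT, FIT vs GAE) on FDI and pain at T4 through each mediator measured at T3. Adjust for the T1 outcome and, where one exists, the T1 mediator. Adherence has no T1 value, so that adjustment cannot apply to it. Use the bootstrap and FDR control already planned. Add a sensitivity analysis for mediator–outcome confounding, because mediators are not randomised. Limit accelerometry and biomechanics paths to participants with those data, and report the numbers.

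Keep the within-arm paths as descriptive associations and the cross-arm comparison as moderation; present neither as evidence of treatment mechanism.

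The cost is rewording and some extra modelling, with no new visits. Fewer paths are likely to reach significance, and mediator–outcome confounding remains.

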# 6.5.1 Missing Data Planning and Analyses

Procedures are in place to minimize missing and inappropriate data (i.e., automated query resolution procedures in Medi-Data Rave®). Missing data will be handled via model-based 3-level multiple imputation in Mplus (version 8.10) as follows. Longitudinal growth curve models will be specified at level 1 (i.e. repeated measures [level 1] nested within participants [level 2]), level 2 (participants within cohorts), and at level 3 (cohorts within assessment sites). However, the effects of IV group random assignment will only be estimated within the level 1 growth curve model. The default potential scale reduction (PSR) value of 1.05 that determines convergence will be over-ridden and PSR = 1.01 will define convergence owing to model complexity.

10.0 Tables – See below

Variable	FIT Teens (n=X)	CBT (n=Y)	GAE (n=Z)	Overall (N=XYZ)
	M (SD), `%	M (SD), %	M (SD), %	M (SD), %
Child				
Characteristics				
Child Age				
Female (%)				
Ethnicity (%)				
Hispanic				
Non-Hispanic				
Race (%)				
More than one				
Caucasian				
African American				
Asian				
Native Hawaiian/				
Pacific Islander				
American Indian/				
Native Alaskan				
Grade Level (%)				
5 th				
6 th				
7 th				
8 th				
9 th				
10 th				
11 th				
12 th				

## Table 1. Baseline subject characteristics by treatment group and overall

Table 2. Baseline	parent and famil	v characteristics by	v treatment grou	p and overall
	paroni ana nanini		y a oaanone gi oe	p ana ovoran

Variable	FIT Teens (n=X)	CBT ( n =Y)	GAE ( n =Z)	Overall (N=XYZ)
Income		 	(	
<\$24,999				
\$25,000-49,999				
\$50,000-74,999				
\$75,000-99,999				
\$100,000-124,999				
\$125,000-149,000				
> \$150,000				
Not Reported				
Caregiver				
Mother				
Father				
Legal guardian				
Caregiver Education				
< High school				
High school/GED				
Partial College/ Trade School				
College Degree				
Post Graduate				
Insurance				
Private				
Medicare				
Medicaid				
Military				
State Specific				
Indian Health				
Non-Us				
Other				
None				

	Baseline				Post-Treatment					3-Month Endpoint						
			95%	6 CI			95% CI		95% CI				95%	6 CI		
	n	Adj. M	LL	UL	SE M	n	Adj. M	LL	UL	SE M	n	Adj. M	LL	UL	SE M	
Functional																
Disability																
Fit Teens																
CBT																
GAE																
Pain																
Fit Teens																
CBT																
GAE																
Child																
Depression																
Fit Teens																
CBT																
GAE																
Pain																
Catastrophizing																
Fit Teens																
CBT																
GAE																
Fear of																
Movement																
Fit Teens																
CBT																
GAE																
Pain Coping																
Fit Teens																
CBT																
GAE																

## Table 3. Outcome scores at Baseline, Post-Treatment, and Primary (3-month) Endpoint

95% CI = 95% Confidence Interval; Adj. M = Mean values adjusted for covariates; LL = Lower Limit for 95% Confidence Interval; UL = Upper Limit for 95% Confidence Interval;  $SE_M$  = Standard Error of the Adjusted Mean

Table 4.	Outcome	scores at	Follow-Up	Time points	

	6-Month				9-Month				12-Month						
		95% CI 95% CI						95% Cl							
	n	Adj. M	LL	UL	SE M	n	Adj. M	LL	UL	SE M	n	Adj. M	LL	UL	SEM
Functional															
Disability															
Fit Teens															
CBT															
GAE															
Pain															
Fit Teens															
CBT															
GAE															
Child															
Depression															
Fit Teens															
CBT															
GAE															
Pain															
Catastrophizing															
Fit Teens															
CBT															
GAE															
Fear of															
Movement															
Fit Teens															
CBT															
GAE															
Pain Coping															
Fit Teens															
CBT															
GAE															

95% CI = 95% Confidence Interval; Adj. M = Mean values adjusted for covariates; LL = Lower Limit for 95% Confidence Interval; UL = Upper Limit for 95% Confidence Interval;  $SE_M$  = Standard Error of the Adjusted Mean
